12.0 Data Management

- Recruitment projects are housed in REDCap. Only study personnel will have access to the REDCap database while actively enrolling for the study.
- Power analysis: The study was designed primarily to power the analysis of digit force direction. For the primary power analysis, based on previous studies, a clinically meaningful difference in force direction was deemed to be 6° . Reduction of force deviation to a value below $<20^\circ$ is expected to result in increased ability to manipulate objects.¹⁰ The mean force deviation for stroke survivors in Chedoke Hand Stage 2-4 is anticipated to be 25.6° based on our preliminary data.¹⁰ Therefore, a 6° change in force direction is expected to lead to a substantial functional improvement.

Our study is longitudinal with 4 primary time points. In the analyses, an autoregressive (AR(1)) covariance structure will be considered for the within-subject correlations (while other structures will also be examined). For a standard deviation of 6.6° (based on the force direction data in our preliminary study), an alpha level of 0.05, 90% power, and the AR(1) correlation between observations on the same subject of 0.8 (based on the preliminary study), a sample size of 22 participants per group will be adequate to detect a difference of 6° . Adjusting for an expected attrition rate of 15% and screen failure rate of 12%, a sample of 30 per group (for a total of n=60) is planned.

- Analysis: The primary formal analysis for the primary outcome measure will be a repeated measures general linear model with an AR(1) structure (although other structures will be considered and compared). The primary independent variables are group (experimental vs. control), evaluation time (baseline (3rd), 2, 4, and 6 weeks for the primary analyses; all 3 baselines and follow-up will be included in subsequent analyses), and their interaction (group \times evaluation time). In addition, we will include sex as an independent variable along with its interactions to study gender differences. If the group \times evaluation time interaction is significant, then the main alternative hypothesis of interest, that at 6 weeks there is difference between the two groups, will be tested using post-hoc tests. Greater improvement for the experimental than control group will support the hypothesis.

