The time course of the effect will also be examined over the 6-week training period and at follow-up. As digit force direction will be recorded throughout the training sessions, spaghetti plots will be generated over the 18 training sessions along with evaluation sessions to examine a more detailed time course. Also in secondary analysis, other covariates such as initial impairment levels will be included. If missing data arise, multiple imputation methods will be applied under the assumption of missing at random (MAR).

The same analysis approach will be applied to each secondary outcome measure. Bonferroni correction will be applied to adjust for multiple comparisons. Data reduction methods may also be considered.

- **Qualitative Analysis:** Interviews will be audio recorded and transcribed verbatim. Qualitative data will be analyzed using the popular constructivist grounded theory methodology.^{11,12} The 'Framework Analysis' commonly used in applied qualitative research will guide the data analysis process¹³ and includes five key stages: familiarization, identifying a thematic framework, indexing, charting, mapping, and interpretation.^{14,15} Two researchers will conduct a high-level reading of transcripts to consolidate the data into analyzable units.¹⁴ Text segments ranging from a phrase to several sentences may be assigned codes a priori (e.g., areas of significance to this project). Additional codes will be created to capture new themes emerging from the data. Two researchers will independently read approximately 25% of the transcripts to establish inter-rater reliability for the final coding hierarchy that will be applied to analyze the all data. Disagreements in definitions or assignment of codes will be resolved through group discussion and further review of the data to achieve consensus. A thematic codebook will be created to document the final codes. Qualitative memos will be used throughout the analysis to document reflective notes, concepts and themes. Transcripts will be carefully read and coded with the assistance of qualitative data management software, constantly comparing the results against the original text for rigor.¹⁶ From final coded transcripts, text segments will be analyzed using a computational process of queries and comparisons.

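### The main week-6 comparison is reached only through a significant group × time interaction, and the 90% power is not tied to that two-step rule, which gives about 65–71% power if the benefit builds steadily

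*Combined protocol and SAP*

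**What the plan says.** All of this is in section 12.0 (Data Management).

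- **Analysis.** The primary model is a repeated-measures linear model with group, time and their interaction, where time is "evaluation time (baseline (3rd), 2, 4, and 6 weeks for the primary analyses"). The decision rule turns on the group × time term: when this "evaluation time interaction is significant, then the main alternative hypothesis of interest, that at 6 weeks there is difference between the two groups", is tested post hoc. The next sentence words the target as a change: "Greater improvement for the experimental than control group will support the hypothesis".
- **Power analysis.** Using an SD of 6.6° and "an alpha level of 0.05, 90% power, and the AR(1) correlation between observations on the same subject of 0.8", the plan states that "a sample size of 22 participants per group will be adequate to detect a difference" of 6°. The enrolment target comes from "Adjusting for an expected attrition rate of 15% and screen failure rate of 12%, a sample of 30 per group".
- **Correlation.** An AR(1) "covariance structure will be considered for the within-subject correlations (while other structures will also be examined").
- **Time course.** "The time course of the effect will also be examined over the 6-week training period and at follow-up". This is not conditional on the interaction. The secondary outcomes are to be analysed in the same way as the primary.

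**The concern.** The question the trial exists to answer is whether the groups differ at week 6. Under the plan it gets a formal test only after a different and more diffuse test, the interaction across four visits, has succeeded. The power of that first test depends on the shape of the gap over time and on the correlation structure, and the plan fixes neither. It also leaves open whether the second step compares week-6 levels or changes from baseline, and whether 0.05 is one- or two-sided.

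A true 6° benefit, the plan's own meaningful difference, could therefore be present at week 6 and never be formally tested. The reader also cannot tell which test the 90% describes. The same rule carries over to every secondary outcome.

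**Working it through.** **Inputs from section 12.0:** difference 6°, SD 6.6°, AR(1) correlation 0.8 (so 0.8³ = 0.512 between baseline and week 6), α = 0.05, 22 per group, four visits. **Assumptions made here:** two-sided testing, time as categories (3 df), no gap at baseline, a gap of 6° at week 6, sex terms left out.

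**1. Where 22 per group can come from.** For a two-sided single-visit comparison at 90% power, n = 2 × (6.6/6)² × (1.960 + 1.282)² = 25.4 per group, or 26–27. That is not 22. Calculations that do give about 22:

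- a one-sided single-visit t test: 22 (power 0.907);
- a two-sided difference averaged over three visits: variance factor (3 + 4×0.8 + 2×0.64)/9 = 0.831, and 25.43 × 0.831 = 21.1, rounded up to 22 (t-test power 0.898);
- a two-sided difference averaged over four visits: factor (4 + 6×0.8 + 4×0.64 + 2×0.512)/16 = 0.774, giving 20–21 (power 0.92 at 22).

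So 22 is not an arithmetic error, but none of these is the planned decision rule. The inflation to 30 is consistent: 22/(0.85 × 0.88) = 29.4.

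**2. Power of the interaction test (the gate).** With D the vector of group gaps at the four visits and S = 6.6² × R, the noncentrality is

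λ = (n/2) × [D′S⁻¹D − (1′S⁻¹D)²/(1′S⁻¹1)], referred to F with 3 and 126 df.

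For the linear path (0, 2, 4, 6) under AR(1) 0.8, D′R⁻¹D = 48.89, 1′R⁻¹D = 4.00 and 1′R⁻¹1 = 1.333. Hence λ = (11/43.56) × (48.89 − 16/1.333) = 9.32, and power is 0.713. The smallest λ for any path from 0 to 6 is 9.31, at week-2 and week-4 gaps of 2.02 and 3.98, so the linear path is essentially the floor.

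**3. Power of the two-step rule.** This was simulated with 40,000 trials per path and the AR(1) parameters estimated by REML. The gate used 126 df; ranges cover 42 to 126 df for the week-6 test.

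| Gap at baseline, weeks 2, 4, 6 | λ | Gate | Two-step, level | Two-step, change |
|---|---|---|---|---|
| 0, 2, 4, 6 | 9.32 | 0.713 | 0.646–0.651 | 0.705–0.706 |
| 0, 3, 5, 6 or 0, 1, 3, 6 | 10.48 | 0.769 | 0.680–0.697 | 0.744–0.747 |
| 0, 4, 6, 6 | 13.99 | 0.886 | 0.764–0.771 | 0.813–0.819 |
| 0, 6, 6, 6 or 0, 0, 0, 6 | 23.15 | 0.987 | 0.827–0.840 | 0.846–0.858 |
| No gate, any path | – | – | 0.838–0.849 | 0.846–0.857 |

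The gate therefore costs about 20 points (level) or 15 (change) on a linear path, about 7 or 4 for an early plateau, and about 1 or less if the gap is abrupt. With a linear gap it blocks the main test in 1 − 0.713 = 29% of trials.

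**4. Sensitivity.**

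- *One-sided second step:* 68–71% (linear) to 90–91% (abrupt). On a linear path the gate caps power at about 71% whatever the second step is.
- *Denominator df:* with 42 df at both steps, linear power is 62% / 68% (level / change); with unstructured covariance, 61% / 67%.
- *26 evaluable per group* (30 × 0.88 = 26.4, no attrition): 74–79% linear, 89–91% abrupt. The linear gate fails in 21% of trials.
- *Correlation, linear path, level / change:* AR(1) 0.7, 53–54% / 55%; AR(1) 0.9, 80–81% / 94%; constant 0.5, 67–68% / 72–73%; constant 0.8, 84–85% / 99%, which removes nearly all of the gate's cost.
- *Null:* the two-step rule rejects in about 0.6% (level) to 2% (change) of trials.

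**5. Per-group n for 90%, two-sided.** Two-step on a linear path: about 35 (change) or 36–37 (level). Week-6 test without the gate: 26–27. Week-6 test without the gate and with baseline adjustment: about 20–21.

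**The case against.** The strongest reply is that the plan does not say time is categorical. If it were fitted as a linear term, the interaction would have 1 df, and on the linear path its power would be 85–86% at 22 per group, so the gate would cost little in the very case that looks worst. This depends on a less natural reading: the plan lists separate visits and follows the interaction with a post-hoc test at week 6. It is also one more choice the plan leaves open.

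Other points stand in part.

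- An omnibus test before contrasts is conventional and does not inflate type I error. The week-6 estimates will still be described, because the time course is examined unconditionally. The harm is lost power, not bias.
- The documents predict no path, and the linear one is close to the least favourable. It is plausible, though: training is progressive over six weeks, and mildly curved paths do little better (68–75%).
- Twenty-two per group assumes dropouts contribute nothing. Multiple imputation and the permitted use of withdrawn participants' data would recover some information, so the linear figure lies between 65–71% and 74–79%.
- A strong constant correlation would largely remove the cost, but the plan powers on AR(1) 0.8.
- The sex terms in the planned model were not included, so the percentages describe a slightly simpler model.
- The 90% figure is not shown to be wrong for every test. What is shown is that it does not describe the two-step rule on a gradual path.

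**Conclusion.** The concern holds and should be fixed. The conditional wording, and the absence of a named powered test, a sidedness and an effect path, are plain on the page. At 22 per group, the two-step rule has about 65–71% power for a linear gap and 83–86% for an abrupt one. None of the paths examined reaches 90% two-sided at that size under AR(1) 0.8. Two-sided testing alone brings the ungated test down to 84–86%; the rest of the shortfall is due to the gate.

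The wording defect is certain. The percentages depend on two-sided testing, categorical time, AR(1) 0.8, model-based denominator df near 126 for the gate, and a model without sex terms.

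**What to change.** 1. In the Analysis paragraph, name the week-6 between-group contrast from the repeated-measures model as the single primary test, at two-sided 0.05, carried out whatever the interaction shows. State whether it is a level or a change contrast. Keep the interaction and the week-2 and week-4 contrasts as secondary, describing the time course, and state the same rule for the secondary outcomes.
2. In the Power paragraph, restate power for that test with its sidedness: about 84–86% at 22 per group without baseline adjustment.
3. As a separate change to the primary model, adjust for the third baseline, either as a covariate or by constraining the baseline means to be equal across groups. The variance factor becomes 1 − 0.512² = 0.738, and two-sided power at 22 per group rises to about 92–94% under AR(1) 0.8 for any path that reaches 6° (88–89% at AR(1) 0.7; 99% or more at AR(1) 0.9 or constant 0.8).

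Items 1 and 2 cost about one sentence each. Item 3 is a further edit, because the third baseline is currently one of the outcome visits. None of them needs more participants, visits or data. With one primary test, type I error stays near 5% (4.8–5.3% in simulation of the baseline-adjusted test).

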1.0 Objectives / Specific Aims

The objective of this project is to determine if 3D finger force training is an effective tool in restoring hand function post stroke.

Aim 1: Determine the effect of 3D finger force training on behavioral hand function

Hypothesis: Hand function will improve more in the experimental group than the control group.

Aim 2: Determine the effect of 3D finger force training on finger force direction control

Hypothesis: The experimental group will achieve greater ability to direct finger force than control after the training.

Aim 3: Determine the biomechanical mechanisms underlying improvement in force direction control

Hypothesis: The training results in improved muscular coordination.

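### The deciding test, an unadjusted week-6 group difference run only after a significant interaction, does not match the stated conclusion of greater improvement, and the two-step rule costs power

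*Combined protocol and SAP*

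**What the plan says.** Section 12.0 (Analysis) fits a repeated measures model with group, evaluation time and their interaction. The third baseline is one of the four outcome time points, with weeks 2, 4 and 6. If the interaction is significant, "the main alternative hypothesis of interest, that at 6 weeks there is difference between the two groups, will be tested using post-hoc tests". The next sentence is "Greater improvement for the experimental than control group will support the hypothesis".

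No contrast is written out. The third baseline is an outcome in this model, not a covariate, and initial impairment enters only in secondary analysis. Section 12.0 applies the same approach to every secondary outcome.

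The aims in section 1.0 are worded both ways. Aim 1 is about change: "Hand function will improve more in the experimental group than the control group". Aim 2, on force direction, speaks of ability after training, which is closer to a level.

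The sample size in section 12.0 rests on "an alpha level of 0.05, 90% power", an SD of 6.6° and an AR(1) correlation of 0.8, and concludes that "a sample size of 22 participants per group will be adequate to detect a difference of 6" degrees.

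**The concern.** Three consecutive steps concern three quantities. The interaction asks whether the arms change differently at any of four visits, in any direction. The post-hoc test asks whether the arms differ in level at week 6. The conclusion is about improvement from baseline.

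Level and change have the same expected value under randomisation, but in a single trial they differ by whatever chance gap exists at the third baseline. With about 22 per arm that gap is often not small. A trial may therefore be significant on one contrast and not the other, and the text leaves room to argue for either once the data are seen. Requiring a significant 3-df interaction before the week-6 test is a second hurdle, and it costs power for the one comparison that the plan calls its main hypothesis.

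**Working it through.** **Inputs** (section 12.0 unless noted)
- True difference 6°; 22 per arm; alpha 0.05, sidedness not stated, taken as two-sided.
- SD: "For a standard deviation of 6.6° (based on the force direction data in our preliminary study"), taken as the SD at each visit.
- Correlation: "the AR(1) correlation between observations on the same subject of 0.8", taken as 0.8 between adjacent visits. Baseline to week 6 is three steps, so r = 0.8³ = 0.512.
- Equal allocation (section 10.0).
- The path of the arm difference at weeks 2 and 4 is not given. Three paths (baseline, weeks 2, 4, 6) are assumed: linear (0, 2, 4, 6), early step (0, 6, 6, 6) and late step (0, 0, 0, 6).

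**The plan's own sample size.** Per arm, n = 2f × [6.6 × (1.960 + 1.282) / 6]² = 25.43f, where f is the variance of the contrast relative to a single visit.
- Mean of the three post-baseline visits, AR(1): f = [3 + 2(0.8 + 0.8 + 0.64)]/9 = 0.831, n = 21.13, so 22.
- Mean of all four visits, constant correlation 0.8: f = (4 + 12 × 0.8)/16 = 0.85, n = 21.61, so 22.
- Week-6 level: f = 1, n = 25.43, so 26 (one-sided, 21).
- Week-6 change: f = 2(1 − 0.512) = 0.976, n = 24.82, so 25.
- Baseline-adjusted week 6: f = 1 − 0.512² = 0.738, n = 18.76, so 19.

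The stated 22 is thus reproduced by a time-averaged difference, not by a two-sided week-6 level or change contrast. Inflation gives 22/(0.85 × 0.88) = 29.4, so 30 per arm, as stated.

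**Baseline imbalance.** SE of the baseline mean difference = 6.6 × √(2/22) = 1.99°. Under simple randomisation it exceeds 2° in 31% of trials. A 2° gap carries forward 0.512 × 2 = 1.02° into the week-6 level difference. The change contrast subtracts the full 2°, so it over-corrects.

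**Power of each week-6 contrast alone at 22 per arm**

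| Contrast | SE | Normal approximation | Simulated |
|---|---|---|---|
| Level | 1.99° | 85.4% | 84% |
| Change | 1.99 × √0.976 = 1.97° | 86.3% | 85% |
| Baseline-adjusted | 1.99 × √0.738 = 1.71° | 94% | 92% |

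**Disagreement between level and change, without the interaction step.** The two z-statistics have correlation (1 − r)/√[2(1 − r)] = 0.494. Both are significant in 77.0% of trials, so they disagree in 85.4 + 86.3 − 2 × 77.0 = 17.7% (17.8% before rounding). Simulated t-tests give 19–20%.

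**With the interaction step (simulated, AR(1) 0.8)**

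| Assumed path | Disagree, among trials with a significant interaction | Interaction and level both significant |
|---|---|---|
| Linear | about 10% | about 65% |
| Early or late step | about 19% | about 83% |

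The linear figure of 65% falls to 61% if the interaction is tested with an unstructured covariance (Hotelling). That test is itself significant in only 68% of linear-path trials, against 98% under an early step.

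**Sensitivity.** With constant correlation 0.8 in place of AR(1), disagreement is about 16% with or without the interaction step. Nearly all of it is change significant and level not, and change power exceeds 99%. With 30 per arm analysed, disagreement under AR(1) without the interaction step falls to 8.5%.

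**The case against.** The strongest case is that the plan is sounder than its wording. A post-randomisation comparison of levels is a legitimate estimate of the treatment effect, improvement can simply name its direction, and Aim 2 is itself worded as ability after training. All of this stands: the level test is not biased.

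A reader might infer that improvement is never tested. The documents do not support that. With a baseline visit among the four time points, the required interaction is a test of differential change, though an unspecific one.

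A reader might also infer that the plan invites false claims driven by baseline imbalance. With no true effect, a significant interaction and level without a significant change occurs in only about 0.1–0.2% of simulated trials. With a linear 6° effect it is under 1%. With an early step it is about 9%, but there the improvement is real. Stratified blocks on Fugl-Meyer (section 10.0) may also make imbalance smaller than the 31% figure suggests.

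Finally, the figure of about one in five should not be read as the plan's own error rate. It describes two week-6 tests taken alone; after the interaction step the range is about 10% to 19%.

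What remains is that no contrast is named, the literal test differs from the literal conclusion, and nothing elsewhere in the document settles which decides.

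**Conclusion.** The point holds as a mismatch between the deciding test and the stated conclusion, together with a loss of power from the two-step rule. It does not hold as a claim of bias or of false conclusions.

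The loss is largest under a linear path: about 65% for the rule as written, against about 85% for the change contrast alone and about 92% for a baseline-adjusted week-6 difference. Under a step path the rule reaches about 83%, close to the level test alone, and the remaining gain comes from baseline adjustment. Replacing the level by the raw change contrast gains almost nothing in precision at r = 0.512 (variance factor 0.976).

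These sizes rest on two-sided 0.05, 22 analysed per arm, SD 6.6° at every visit, AR(1) 0.8 and the assumed paths. The plan says other covariance structures will be considered, and a slower decay of correlation favours change or adjustment over the level test more strongly. The matter should be settled before the data are seen, but it does not threaten the trial's validity.

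**What to change.** In section 12.0, pre-specify one week-6 contrast as the sole basis for declaring the hypothesis supported, not conditional on the interaction test. Preferably this is the week-6 group difference adjusted for the third-baseline value. Otherwise it is the group by time contrast from third baseline to week 6 in the model already planned. Because the model includes sex and its interactions, state that the contrast is averaged over sex, and state the sidedness.

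Word the conclusion to match the contrast chosen, use the same contrast for each secondary outcome, and report the overall interaction and unadjusted week-6 levels descriptively.

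The cost is one SAP sentence and one contrast statement, with no new data and no change in sample size. A single pre-specified test holds the nominal 5% error rate; the two-step rule is stricter because both tests must be significant, and that extra strictness is given up. If the raw change contrast is chosen, it is less precise than the level test whenever the baseline to week-6 correlation is below 0.5. Baseline adjustment avoids that.

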10.0 Study Design / Methods

- **Study design:** The study will be a randomized controlled trial. Subjects will be randomly assigned to either the experimental or control group using block randomization to ensure balance (half in the experimental, half in the control). Block sizes will be random (4, 6, or 8). The block randomization will be stratified equally by the moderate vs. severe impairment level (with the Fugl-Meyer Upper Extremity assessment cut-off score of 19⁹).
- **Intervention schedule:** All subjects will undergo approximately two-hour force training, 3 times per week for 6 weeks. The experimental group will practice for various target force direction to explore the 3D force workspace and receive explicit feedback in 3D force, while the control group will receive feedback in 1D on a computer screen (in target direction only with no explicit feedback on other directions, thus no training in force directional control, much like simple squeeze ball repetitions). The training dose will be controlled by having a minimum of 8 sets with 14 targets each (a total of 112 targets) per session, with maximum 30 sec allowed for each target (up to 56 min/session).
- **Evaluations:** Outcome measures will be assessed at baseline, immediately after 2 and 4 weeks of force training, at post (within a week after 6-wk force training), and 1 month after training ends (i.e. follow-up to assess retention). The baseline measurement will take place 3 times over 3 weeks prior to training to examine the baseline recovery rate. Each evaluation visit will take 1-5 hours. Evaluation for each outcome is detailed below.

- Behavioral hand function: Subjects' upper extremity function will be assessed using conventional clinical assessments used in occupational/physical therapy in which participants will be asked to move the affected hand and arm, grasp objects and perform prescribed tasks (e.g., lifting an object off the table, releasing the object into a bin, gripping hard, reaching as high or far as possible, opening the hand as much as possible). These tests will be videotaped for scoring. The joint positions and muscle activity during these tasks will also be recorded. The behavioral hand function assessments will last approximately 1 hr.

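### Holm step-down in place of Bonferroni, on the same family of tests, would add a little power at no cost in familywise error; the family itself still has to be stated

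*Combined protocol and SAP*

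**What the plan says.** All references are to the combined protocol and SAP.

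- **Section 1.0 (Objectives / Specific Aims):** the overall purpose is stated as "The objective of this project is to determine if 3D finger force training is an effective tool in restoring hand function post stroke". The Aim 1 hypothesis is "Hand function will improve more in the experimental group than the control group".
- **Section 10.0 (Evaluations):** "upper extremity function will be assessed using conventional clinical assessments used in occupational/physical therapy". Assessments are in the plural; no instruments are listed here.
- **Section 12.0 (Power analysis):** "The study was designed primarily to power the analysis of digit force direction". No effect size, SD or power is given for hand function.
- **Section 12.0 (Analysis):** if the group by "evaluation time interaction is significant, then the main alternative hypothesis of interest, that at 6 weeks there is difference between the two groups", is then tested post hoc. On the remaining outcomes and multiplicity, the plan states: "The same analysis approach will be applied to each secondary outcome measure. Bonferroni correction will be applied to adjust for multiple comparisons". It leaves a further option open in the sentence after that: "Data reduction methods may also be considered".

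The text does not list the secondary outcomes or give their number. Nor does it say whether the comparisons being adjusted are the outcomes, the post-hoc tests, or both.

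**The concern.** The trial is sized on force direction, while its objective is hand function. If the hand-function assessments sit in the adjusted family, each must pass 0.05/k, where k is the number of tests, however strong the other results are. Holm uses that threshold only for the smallest p-value and relaxes it after each rejection. When several outcomes improve together, Bonferroni therefore gives up some power on the tests that answer the objective, with nothing gained in error control.

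Joint improvement is a plausible case here, since the power analysis expects a change in force direction to bring functional improvement.

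**Working it through.** **1. The plan's own figure.** For force direction (section 12.0): difference 6°, SD 6.6°, alpha 0.05 (taken as two-sided), power 90%, correlation 0.8, four time points.

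- Without repeated measures: 2 × (1.960 + 1.282)² × (6.6/6)² = 25.4 per group.
- Factor for the mean of four visits at constant correlation 0.8: (1 + 3 × 0.8)/4 = 0.85, so 25.4 × 0.85 = 21.6, rounded up to 22. This matches the plan. An AR(1) mean of all four visits (factor 0.774) gives 20; an AR(1) mean of the three post-baseline visits (factor 0.831) gives 22.
- Inflation: 22/(0.85 × 0.88) = 29.4, rounded up to 30. This also matches.

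The check supplies 22 evaluable per group and 6/6.6 = 0.91 SD. The latter belongs to force direction and is only borrowed below for the other outcomes.

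**2. The two rules on one family of k p-values.** Bonferroni rejects when p ≤ 0.05/k. Holm orders the p-values and compares them in turn with 0.05/k, 0.05/(k−1), …, 0.05, stopping at the first failure. For k = 3, Bonferroni uses 0.0167 three times and Holm uses 0.0167, 0.025 and 0.05. No Holm threshold is below Bonferroni's, so every Bonferroni rejection is also a Holm rejection. The 0.05 bound for Holm holds under any dependence. Setting a p-value to 1 when the interaction gate fails only enlarges it, so the bound is unaffected.

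**3. Size of the gain.** The documents give no k, effects or between-outcome correlation for these outcomes, so all are assumed: k = 3, 5 or 8; correlation 0.5 between outcomes; AR(1) 0.8 over four times; differences growing linearly to week 6. Each outcome has an interaction F test at 0.05 as gate, then a week-6 t test on 42 df (40,000 simulated trials per case). Power per improving outcome, Bonferroni / Holm:

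| Case | k = 3 | k = 5 | k = 8 |
|---|---|---|---|
| All improve 0.91 SD | 53.1 / 56.8% | 48.6 / 53.7% | 44.6 / 50.6% |
| About half improve 0.91 SD (2, 3, 4) | 53.7 / 55.4% | 49.2 / 51.3% | 44.3 / 46.2% |
| Exactly one improves 0.91 SD | 52.9 / 52.9% | 49.1 / 49.1% | 44.6 / 44.6% |
| All improve 0.5 SD | 9.2 / 9.9% | 7.4 / 8.1% | 6.2 / 6.8% |

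No case produced a rejection by Bonferroni that Holm missed.

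**4. Sensitivity, all improving 0.91 SD.**

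- Most of the effect early (60%, 90%, 100% at weeks 2, 4, 6): 59.3 / 64.4%, 54.0 / 60.8%, 48.8 / 56.7%, a gain of 5 to 8 points.
- Week-6 test on change from baseline: 64.1 / 65.7%, 61.1 / 64.3%, 56.9 / 62.4%, a gain of 1.6 to 5.5 points.
- Family of three time contrasts (assumed weeks 2, 4, 6) within one outcome, at week 6: 53.3 / 53.5% with linear growth and 59.4 / 61.3% with early effect.
- No gate, simple z-tests with 50 to 90% unadjusted power, 2 to 10 outcomes, correlation 0 or 0.5: gains of 2.3 to 14.6 points if all improve, 0.8 to 3.9 if about half do, and at most 0.3 if one does.

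**5. Familywise error.** Under the global null with the gate, both rules give 0.007 to 0.008. In an adverse case (about half the outcomes improving 1.82 SD, the rest differing only at weeks 2 and 4), Bonferroni / Holm give 0.017 / 0.049, 0.019 / 0.046 and 0.022 / 0.044 for k = 3, 5 and 8. Holm uses more of the allowance but stays within it.

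**The case against.** Bonferroni is a legitimate choice with simple simultaneous confidence intervals, and keeping it leaves nothing invalid. That stands, and it limits the point to an optional improvement.

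The premise is inferred twice: that hand function is a secondary outcome, and that the adjustment runs over outcomes. Both inferences may fail. If only post-hoc time contrasts were meant, the week-6 gain shrinks to 0.2 to 2 points. The gains also rest on an effect borrowed from force direction, and the ungated figures support the direction of the gain but not the gated size.

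Four stronger readings are tempting, and the documents do not support them:

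- *The plan demotes its own objective by making hand function secondary.* No section says so. Section 12.0 says only which outcome drove the power calculation.
- *If only hand function improves, Holm gains nothing.* This is true only if hand function is one test. Section 10.0 describes several assessments. With three improving hand tests in a family of five, power is 49% under Bonferroni and 51% under Holm.
- *Holm would make hand function well powered.* In the all-improve case at 0.91 SD, power with neither gate nor correction is 84%, with the gate alone 61%, and with gate and Bonferroni at k = 3 53%. The gate costs 84 − 61 = 23 points; Holm returns about 4 and does not touch the gate.
- *Any use of Holm keeps 0.05.* The guarantee is for one family. Outcomes in one family at 0.05 and time contrasts in another at 0.05 are bounded overall only by 0.05 + 0.05 = 0.10. Dominance over Bonferroni likewise requires the same p-values.

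**Conclusion.** The point holds as an efficiency improvement, not as an error. That Holm is never worse than Bonferroni on the same p-values and family, and stays within 0.05, rests on no assumption about effects or correlation.

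The size of the gain does rest on assumptions. In the base cases it is about 4 to 6 points per improving outcome if all improve by 0.91 SD, about 2 points if about half do, under 1 point if all improve by 0.5 SD, and zero if exactly one outcome in the family improves. Confidence in the direction is high. Confidence in the size, and in how far it reaches hand function, is moderate at best, because the family, the effects and the correlations are not given. The 0.05 bound does not extend to the separate test of the outcome the trial is powered on. The sample size does not change.

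**What to change.** In section 12.0 (Analysis), replace the Bonferroni sentence with: *Multiple comparisons will be adjusted by the Holm step-down procedure at two-sided familywise 0.05, applied to the same p-values and the same single family for which Bonferroni was intended.* Then:

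- List that family before unblinding and after any data reduction.
- If both secondary outcomes and post-hoc time contrasts were meant, put them in one Holm family. Do not run separate families at 0.05 each.
- If the p-value used is the post-hoc week-6 test, set it to 1 when that outcome's group × time interaction is not significant.

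The cost is analysis wording and a decision by the sponsor on the family, with no new data, visits or participants. Two downsides remain: simultaneous confidence intervals that match Holm are less simple than Bonferroni's, and attained familywise error can lie nearer to 0.05. A sponsor who prefers Bonferroni for its intervals can keep it, but should still state the family.
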